5.5.2 REPEATED SCREENING VISITS (VISIT 0/R1)

In some circumstances a repeated screening may need to be scheduled. Examples include, but are not limited to:

- 1. Incomplete information available at time of screening to determine eligibility (e.g. current lens brands worn, history from current eye care practitioner etc.)
- 2. Study procedures unable to be completed in time scheduled for visit;
- 3. Required study lenses not available at the time of the screening visit;
- 4. A transient health condition which may affect the eye(s) (e.g. a common cold, active allergies, fatique etc.)
- 5. The short-term use of medications (e.g. antibiotics, antihistamines etc.)
- 6. Reassessment of baseline ocular conditions (e.g. corneal and/or conjunctival staining, scars etc.)

[figure not shown]
The maximum total number of screenings permitted will be 3, the initial and two repeat screening visits.

[figure not shown]
5.5.3 VISIT 1-0 DISPENSE LENS TYPE #1

This visit may or may not be subsequent to the screening visit, depending on lens availability (only lenses from commercial 6-pack boxes are used for dispensing) but will occur no later than 28 days after Visit 0 (or 0/R1). Participant to attend this visit wearing spectacles if this visit is scheduled on a different day as Visit 0 (or 0/R1).

The study procedures are outlined below:

1. Confirm participant's health and medications are unchanged.

11. Confirm that Visit 2-0 is scheduled 28-32 days after this Visit 1-0.

5.5.4 VISIT 2-0, 1-MONTH FOLLOW-UP LENS TYPE #1, DISPENSE LENS TYPE #2

Participants will be asked to arrive having worn Lens type #1 for at least 2 hours prior to the visit. This visit will occur 28-32 days (inclusive) after visit 1-0.

The study procedures are outlined below:

- 1. Confirm participant's health and medications are unchanged.
- 2.
- 3.
- 4.

[figure not shown]
12. Confirm that Visit 3-0 has been scheduled 28-32 days after this Visit 2-0.

5.5.5 VISIT 3-0 1-MONTH FOLLOW-UP LENS TYPE #2

Participants will be asked to arrive having worn Lens type #2 lenses for at least 2 hours prior to the visit. This visit will occur 28-32 days (inclusive) after visit 2-0.

The study procedures are outlined below:

- 1. Confirm participant's health and medications are unchanged.
- 2.

5.5.6 STUDY EXIT

The study exit form will be completed when a participant exits the study. This form will be completed either after the last study visit, or if the participant is discontinued from the study at another time, complete also an unscheduled visit form. A study exit form must be completed for all participants who have taken a study ID number. If in the opinion of the investigator post-study follow-up visits are required, the exit form will be completed after the last follow-up visit.

Exit visual acuity will be recorded with either the participant's spectacles, refraction or habitual contact lenses. An exit biomicroscopy assessment will be conducted if not already completed on the same day for a concurrent study visit.

After the exit assessments have been completed, the participant and investigator will complete the study completion and remuneration forms. At this time the participant will be considered as having exited the study.

5.5.7 UNSCHEDULED VISITS

An unscheduled visit is defined as an interim visit requested by the participant or investigator due to an unanticipated problem. Data recorded at these visits will be entered into the database. Only relevant and applicable unscheduled visit information will be included in the final report as deemed necessary.

5.6 STUDY PROCEDURES

Table 4 summarizes the procedures conducted at each visit.

Table 3: Summary of procedures to be conducted at scheduled visits

	0 Screen Fit & order study CL	1-0 Dispense first study lens	2-0 1-month follow- up first study lens, dispense second study lens	3-0 1-month follow- up second study lens	Exit
Consent process	x				
Subject age & sex	x				
CL history and/or lens wear schedule	х		х	х	
Health & medication	x	Х	Х	Х	

	0 Screen Fit & order study CL	1-0 Dispense first study lens	2-0 1-month follow- up first study lens, dispense second study	3-0 1-month follow- up second study lens	Exit
Review any problems with eyes/study lenses	Study OL	х	lens X	х	
	х				X (or V1 subj. refraction result)
	Х				
	х				
Study lens fitting	Х				
Dispense study CLs		Х	Х		
	Х	Х	Х	Х	
	Х	Х	Х	Х	
	Х		Х	Х	
	Х		Х	Х	
				Х	
	Х		Х	Х	
		Х	Х		
			х	х	
	х	х	х	х	X (unless completed at concurrent visit)
Study completion and Exit					Х

¹ High Contrast High Illumination

5.6.1 STUDY LENS FITTING

Both lens types will be fit according to the manufacturers fitting guide, using the vertex-corrected spectacle refraction as a guide.

5.6.2			

5.6.3 LENS FIT ASSESSMENT

Post-blink movement (0-4 descriptive scale, 1 step)

- 0 insufficient, unacceptable movement
- 1 minimal, but acceptable movement
- 2 optimal movement
- 3 moderate, but acceptable movement
- 4 excessive, unacceptable movement

Lens centration (1-4 descriptive scale, 1 step)

- 1 perfectly centred
- 2 slightly decentred
- 3 markedly decentred but corneal coverage
- 4 unacceptable decentration showing corneal exposure

Rotation of the inferior toric mark: three response options, two with degrees to be measured by estimation or slit-lamp protractor:

- i. optimal (ie. toric mark stabilizes exactly at 6 o'clock)
- ii. toric mark stabilizes to rest nasal to the 6 o'clock position; include the number of degrees from 6 o'clock position
- iii. toric mark stabilizes to rest temporal to the 6 o'clock position; include the number of degrees from 6 o'clock position

Overall lens fit acceptability:

• Is the lens fit clinically acceptable? Yes / No

6 MONITORING PROTOCOL ADHERENCE

Adherence to study visit windows, lens wearing schedule, and time windows around other data collection points (i.e. subjective ratings) will be monitored by CORE. Deviations from the study plan as described in the protocol will be reported in the study report. As described in Section 13.4,

major protocol deviations will be reported to the Sponsor and Sterling Institutional Review Board within 10 days of becoming aware of them (as per Sterling Institutional Review Board guidelines).

7 POTENTIAL RISKS AND BENEFITS TO HUMAN PARTICIPANTS

There may be no direct benefits to the subjects in this study. Participation in a study may contribute to scientific research information that may be used in the development of new contact lens products. The subjects will receive an examination of the front part of their eyes and may have the opportunity to try a different type of soft contact lenses and/or different lens care products at no cost to them. The contact lens materials used in this study are commercially available as daily wear. This study will investigate participants' wearing schedule intended for daily wear (NOT extended wear), similar to the average wearing time of 10-16 hours for daily wear lenses.

All lenses used in this study are IDE exempt under 21 CFR 812.2(c)2. The two study contact lens types will be worn as per their approved use; on a daily wear basis with monthly replacement. When contact lenses are worn on a daily wear basis there is a small risk of an adverse event compared to not wearing contact lenses. When contact lenses are worn on an extended wear basis, there is a significantly increased risk of an adverse reaction compared with wearing contact lenses on a daily wear basis.

Adverse events and/ or complications in daily wear of soft contact lenses can occur (e.g.: inflammation and infection). Complications that may occur during the wearing of contact lenses include discomfort, dryness, aching or itching eyes, excessive tearing, discharge, hyperemia and variable or blurred vision. More serious risks may include pain, photophobia, iritis, corneal edema or eye infection. Although contact lens-related infections are very infrequent, the possibility does exist. The incidence of infection due to day-wear soft lenses is 0.035%. Almost always an infection will occur only in one eye. This risk is assumed by 35-million Americans who currently wear contact lenses and only current soft lens wearers will be recruited for this study.

A dye (fluorescein) normally used for eye examinations is being used in this study. Although rare, it is possible to have an allergic reaction to the dye. Participants will be asked if they have a known allergy or sensitivity to fluorescein.

The assessments conducted in this study are routine clinical procedures and they include autorefraction, auto-keratometry, visual acuity, anterior ocular health assessment, and contact lens fitting will be used. In addition, high magnification imaging of the lens fit may be made using 35 mm or digital cameras. Patients will be monitored frequently until the end of the study to reduce the occurrence of adverse or potential adverse events. Patients will be given instructions from their investigator regarding early symptoms and signs of adverse events.

8 ADVERSE EVENTS

See CORE SOP012 for a description of all adverse events, including management and reporting. An 'adverse event' refers to any undesirable clinical occurrence in a participant, whether it is considered to be device-related or not. Adverse events (AE) may be classified as 'unanticipated adverse device effects,' 'serious adverse events,' 'significant adverse events,' or 'non-significant adverse events,' as defined below, Table 5.

A number of conditions may result in temporary suspension until resolution. These include corneal infiltrates, corneal staining, limbal injection, bulbar injection or tarsal conjunctival abnormalities.

Table 4: Classification of types of adverse event

Classification	Definition
Serious Adverse Event	Those events that are life-threatening, or result in permanent impairment of a body function, or permanent damage to a body structure or necessitate medical (therapeutic) or surgical intervention to preclude permanent impairment of a body function or permanent damage to a body structure.
Significant Adverse Event	Those non-serious adverse events that occur with contact lens usage that are not sight-threatening but are usually symptomatic and may warrant therapeutic management and /or temporary or permanent discontinuation of contact lens wear.
Non-Significant Adverse Events	Those less severe non-serious adverse events that occur with contact lens usage that are not sight-threatening, may or may not be symptomatic and may warrant palliative management, such as ocular lubricants or temporary interruption of contact lens wear.
Unanticipated Adverse Device Effect	Adverse events in a study that were not previously identified in the protocol in terms of nature, severity, or degree of incidence. An Unanticipated Serious Adverse Device Effect is an unanticipated adverse event that is serious in nature and caused by or associated with the device and is considered reportable.

AE classification, coding (for reporting to the sponsor) and reporting details, plus examples, are provided in Table 6.

Table 5: Contact lens adverse event classification, coding and reporting guide

Code	Condition	Reporting
Serious		
01	Presumed infectious keratitis or infectious corneal ulcer	For all serious
02	Permanent loss of ≥ 2 lines of best spectacle corrected visual acuity (BSCVA)	AEs:

03	Corneal injury that results in permanent opacification within central cornea (6mm)	Notify sponsor as
04	Uveitis or Iritis (e.g. presence of anterior segment inflammation as described in ISO 11980, Annex B)	soon as possible, within 24 hours;
05	Endophthalmitis	ORE reporting will be within 24
06	Hyphema	hours as per requirements
07	Hypopyon	roquiromonio
08	Neovascularization within the central 6mm of cornea	
00	Other serious event	
Signific	cant Adverse Events	
11	Peripheral (outside central 6mm), non-progressive, non-infectious ulcer	
12	Symptomatic corneal infiltrative event	
13	Superior epithelial arcuate lesions (SEALs) involving epithelial split	
14	Corneal staining ≥ dense coalescent staining up to 2mm in diameter (e.g. moderate, ISO 11980 grade 3)	Notify sponsor as soon as possible, within 5 working
15	Corneal neovascularization ≥ 1.0mm vessel penetration (e.g. ≥ ISO 111980 Grade 2), if 2 grade change from baseline	days; ORE reporting as per requirements
16	Any temporary loss of ≥ 2 lines BSCVA for ≥ 2wks	requirements
17	Any sign and/or symptom for which participant is administered therapeutic treatment or which necessitates discontinuation of lens wear for ≥ 2 weeks	
10	Other significant event	
Non-si	gnificant Adverse Events	
21	Conjunctivitis (bacterial, viral or allergic)	
22	Papillary conjunctivitis if ≥ mild scattered papillae/follicles approximately 1mm in diameter (e.g. ISO 11890 Grade 2), if 2 grade change from baseline	Notify sponsor as
23	Asymptomatic corneal infiltrative events	soon as possible, within 5 working
24	Any sign and/or symptom for which temporary lens discontinuation for > 1 day is recommended (if not already classified)	days; ORE reporting as per requirements
20	Other sign and/or symptom warranting classification as a non-significant adverse event	

8.1 NORMAL OR ADAPTIVE SYMPTOMS

Transient symptoms such as end-of-day dryness, lens awareness, itching or burning or other discomfort may occur with contact lens wear and may occasionally reduce wearing time. These are not reported as adverse events unless in the investigator's opinion they are unexpected in nature, severe or have a high rate of occurrence.

8.2 PROCEDURES FOR ADVERSE EVENTS

[figure not shown]
Treatment of an adverse event will depend on its nature and severity. Based on the clinical judgment of the investigator the ocular adverse events may be managed at the practice, or the participant may be referred to another eye care practitioner for treatment. The investigator will attempt to determine whether the reaction is related to the test device or a result of other factors. An adverse event form will be completed for each adverse event. If both eyes are involved, a separate adverse event form will be completed *for each eye*. Whenever possible, the adverse event will be photo-documented.

Expenses incurred for medical treatment as part of study participation will be paid by the sponsor (bills and prescription receipts kept). The participant must be followed until resolution or no further change is anticipated and/or referred for further care with the appropriate health care professional and/or recorded as being under appropriate health care as per investigator's discretion. A written report will be completed indicating the subsequent treatment and resolution of the condition.

8.3 REPORTING ADVERSE EVENTS

All potential Serious and Unanticipated Adverse Device Effects that are related or possibly related to participant's participation will be reported to CORE's lead study coordinator (details below) and also to the sponsor (details below) within 24 hours of the investigator becoming aware of the event. The site's Principal Investigator will also report the event to Sterling IRB within 10 days of becoming aware of the Serious or Unanticipated event, using the Reportable Events Form. All fatal or life-threatening events will be reported immediately to the IRB.

Significant and Non-Significant Adverse Events will be reported to CORE's lead study coordinator and the sponsor as soon as possible, but no later than 5 working days after becoming aware of the occurrence.

Details of all adverse events will be included in the study report.

9 DISCONTINUATION FROM THE STUDY

Participants may be discontinued at the discretion of the investigator or sponsor in consideration of participant safety or protocol compliance, or at discretion of the participant. Participants discontinued from a study will be reimbursed for their active involvement in the study (including the initial screening visit and all lens fitting visits) as per the information on the consent letter. Upon discontinuing, a participant will be offered the option of their data being withdrawn from future statistical analysis. The following is a list of possible reasons for discontinuation from the study:

- Screening failure: Participants will be discontinued if they do not meet the inclusion and exclusion criteria outlined in section 5.2.3.
- Unacceptable performance with products to be used in study: Participants may be discontinued if they are unable to achieve acceptable comfort and /or vision with the study products.
- Positive slit lamp finding: Participants may be permanently discontinued from the study depending on the severity of the condition and on the judgement of the investigator.
- Adverse event: If a participant experiences an adverse event during the study, they may
 be discontinued based on the clinical judgement of the investigator.

- Symptoms: If the participant has persistent symptoms, they may be discontinued based on the clinical judgement of the investigator.
- Disinterest, relocation or illness: The participant may choose to discontinue due to reasons within or beyond their control.
- Violation of protocol or non-compliance: The participant will be discontinued if they are unable or unwilling to follow the protocol specified visit schedules and/or study procedures.
- Instillation of topical ocular medication: The participant will be discontinued if they elect
 to use a topical ocular medication during the study unless that topical ocular medication
 is prescribed for a limited duration (less than two weeks) to treat a transient condition; in
 this case the participant may remain an active participant (at the discretion of the
 investigator) after stopping topical ocular medication following resolution of the ocular
 condition).
- Lost to follow-up: The participant will be discontinued if they cannot be contacted and do
 not return to complete the final study exit, and if the investigator has made a reasonable
 effort to contact the participant for a final study visit.
- Premature termination of the study by the sponsor, CORE or Sterling IRB.

A discontinuation form, stating the reason for discontinuation will be completed, which requires the signatures of both the participant and the investigator except where the participant is lost to follow-up in which case only the signature of the investigator is required.

When a participant chose to discontinue from the study, they will be given the opportunity to withdraw their data from the statistical analysis. This choice will be captured on the discontinuation form.

All discontinuations including their reasons will be included in the final report.

10 DEVICE MALFUNCTIONS

A device malfunction means the failure of the device to meet its performance specification or otherwise perform as intended. Any defective lens that is *likely* to cause or contribute to a *Serious Adverse Event* should be reported to CORE and the sponsor **within 24 hours** of the investigator becoming aware of the malfunction. Sterling IRB would also be notified within 24 hours of any device malfunction that may contribute to a *Serious Adverse Event*.

Other defective lenses should be reported to CORE as soon as possible.

This clinical study will also ascertain satisfaction or preference with subjective attributes such as comfort, vision, or lens handling. Responses to these subjective questionnaires will not be considered as complaints or device malfunctions.

11 STUDY COMPLETION AND REMUNERATION

At the last scheduled protocol visit a study completion form will be completed, which requires the signatures of both the participant and the investigator. Participants will also be provided with a letter of appreciation.

Once their involvement in the study is complete, participants will be informed about receiving feedback following study completion in the Letter of Appreciation.

Participant remuneration will be paid as per site contract and approved consent letter.

12 STATISTICAL ANALYSIS AND DATA MANAGEMENT

12.1 STATISTICAL ANALYSIS

All data will be analyzed by CORE at the University of Waterloo. Unmasked data analysis will be conducted using Statistica 14.0, Statsoft or other suitable software. Descriptive statistics will be provided on demographic data (age, gender, refractive error distribution, etc.). Table 7 lists the primary and other outcome variables and anticipated statistical procedures.

Visual acuity results will be converted to LogMAR for analysis purposes.

Comparisons will be made between the study lenses for the variables measured at the 1-month visits. Additionally, the subjective ratings completed on days 7, 14 and 27 with each study lens will be compared. A binomial test will be used to analyze the results for the count data of subjective preferences and experience responses. Where relevant, the number of "no preference" responses will be evenly distributed to the two options on the basis they would be equally likely to choose either.

For assessments conducted for each eye separately, the right eye will be used for analysis. If a general difference is found (paired t-test / Wilcoxon matched pairs) between OD and OS, a comment will be provided.

Where appropriate, data may be presented as both mean or median and as counts by 'bucket' groups.

Additional analysis may be conducted.

Table 6: Statistical procedures

Variable	Analysis	Statistical test
	Comparison between study lenses	Freidman ANOVA
	and time points	Wilcoxon matched pairs test
	Comparison between study days	Freidman ANOVA
	and/or between contact lenses per	Wilcoxon matched pairs test
	time point.	RMANOVA
Demographics,	Descriptive stats	One or more: mean,
lens fit variables		median*, mode, standard
		deviation, minimum,
		maximum, frequency count

^{*} For non-parametric data only

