5.1.2 RANDOMIZATION

A randomization schedule will determine the order of Lens A and Lens B wear for the first/second month for each participant. Participants will be randomized immediately prior to their first lens dispense.

This randomization schedule will be generated for each site using a web-based program: (www.randomization.com). The lens type that will be worn during the first month is called "Lens type #1", the lens type dispended for the second month is called "Lens type #2". The final study randomization schedule will be generated by CORE's Database Administrator and provided to the research assistants at each site.

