5.1.3 MASKING

At the fitting visit, only the participant will be masked of the lens type, the investigator will know which type is fit to make changes to the lens at this visit if needed. Strongly adhesive stickers will be placed on the packages/foils to mask the participant to the lens brand. At both dispense visits, participants will be masked to the lens type dispensed. The study personnel will determine the lens order according to the randomization schedule and will over-labeled the lens packages/foils prior to dispense.

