5.5 SCHEDULED AND UNSCHEDULED VISITS

This study has a minimum of 4 scheduled study visits, including the screening visit. There is an option for repeated screening visit if needed.

A scheduled 1-month follow-up visit may only take place when the participant attends wearing the study lenses for at least two hours that day. If this is not the case and the participant is not experiencing any problems with the lenses, the appointment will be rescheduled, ideally within the visit window.

Visits that fall outside of the specified visit windows will be designated as protocol deviations and at the end of the study, the data collected during protocol deviations will be assessed for their suitability to be included in the analysis population.

Table 3 summarizes the scheduled study visits and study codes.

Table 2: Summary of visits

Visit code	Approximate Duration	Visit Description
0	2 hrs	Screening, Habitual baseline (collect in-office ratings for subjective experience, satisfaction and agreement questions) & Fitting of study lenses
0/R1, 0/R2	As needed	Repeat Visit 0 if needed
1-0	0.75 hr	Dispense Lens type #1 (0-28 days after Visit 0); collect in-office subjective ratings after 10 mins of lens insertion; provide at-home diaries
2-0	1.5 hr	1-month follow-up Lens type #1 (28-32 days after 1-0); review at-home diaries; collect in-office ratings for subjective experience, satisfaction and agreement questions for Lens type#1
		Dispense Lens type #2; collect in-office subjective ratings after 10 mins of lens insertion; & Provide at-home diaries
3-0 and exit	1.5 hr	1-month follow-up Lens type #2 (28-32 days after 2-0); review at-home diaries; collect in-office ratings for subjective experience, satisfaction and agreement questions for Lens type#2; collect preference ratings between Lens type#1 and Lens Type#2
		Exit forms & remuneration

Visits 1-0 (Dispense Lens type #1) and 2-0 (Dispense Lens type #2) will count as day 0 Lens type #1 and #2 will be either Lens A or B, as determined by the randomization table.

[figure not shown]

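### The analysis is planned with lens identity visible while several analytic choices stay open; coding the lenses and fixing one primary test in advance would be a cheap safeguard against directional bias.

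*Combined protocol and SAP*

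**What the plan says.** Section 12.1 states the choice outright: "Unmasked data analysis will be conducted using Statistica 14.0, Statsoft or other suitable software". It also says who does the work: "All data will be analyzed by CORE at the University of Waterloo". Section 5.1.2 places the allocation list in the same organisation: "The final study randomization schedule will be generated by CORE's Database Administrator and provided to the research assistants at each site".

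Masking is described in Section 5.1.3 and concerns the participant: "At both dispense visits, participants will be masked to the lens type dispensed". No visible section mentions coded lens labels or a masked analyst.

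These choices remain open at the analysis stage:

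- **Status of the tests.** Section 12.1 says "Table 7 lists the primary and other outcome variables and anticipated statistical procedures" (the table itself is captioned Table 6).
- **Listed tests.** Both comparison rows give Friedman ANOVA and the "Wilcoxon matched pairs test". The second row adds repeated-measures ANOVA. No rule for choosing among them is visible.
- **Further work.** "Additional analysis may be conducted", without limits.
- **Analysis population.** For visits outside their windows, Section 5.5 says that at the end of the study "the data collected during protocol deviations will be assessed for their suitability to be included in the analysis population". It does not say whether that decision is made without knowledge of the lens.

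**The concern.** The primary outcome is a subjective 0 to 100 rating of how easily the lens is removed. Lens A is made by the company that reimburses the sites for study product and registers the trial, taken here to be the sponsor. An analyst who can see which lens is which, and who must still choose a test, a grouping or whether a late visit counts, can be influenced by whether the result suits that company. No intent is needed. A borderline result in the unwelcome direction may simply be examined harder.

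Nothing visible in Section 12.1 needs lens identity. The lens comparisons are made within person between two labels, and the null hypothesis in Section 4 is no difference. Decisions made under the labels X and Y could not lean towards the sponsor's lens.

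**Working it through.** **Inputs from the plan.** 44 completers, 90% power, SD 20 (Section 5.3.1). Two lenses compared within person (Section 5.1.1). Tests as listed in Table 6.

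**The plan's own figure.** The visible text gives no detectable difference, alpha or sidedness, so 44 cannot be rebuilt from stated inputs alone. Assuming two-sided alpha 0.05, SD of within-person differences 20 and a difference of 10, the normal approximation is n = (20 × (1.960 + 1.282) / 10)² = 6.484² = 42.04, rounded up to 43. The paired t-test (noncentral t) gives 44, with power 0.900. The stated number is consistent with those assumptions. The rest of the check uses only n = 44. The three tests do not depend on the scale of the differences, so the SD does not matter here.

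**Simulation.** 20,000 datasets of 44 paired differences, normal, no true difference, nominal two-sided 0.05. With two lenses, repeated-measures ANOVA is equivalent to the paired t-test, and Friedman reduces to the sign test. The Monte Carlo standard error near 5% is √(0.05 × 0.95 / 20,000) = 0.15 percentage points.

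*Assumption.* The listed tests are free alternatives for the primary outcome. This is the worst case.

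*Step 1: one fixed test.* Paired t 4.9%, Wilcoxon 4.8%, Friedman 4.9%.

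*Step 2: identity visible, choice steered by direction.* Report the smallest p-value if Lens A leads and the largest if Lens B leads.

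| Tests open | False finding for A | False finding for B | Total |
|---|---|---|---|
| t, Wilcoxon | 2.7% | 2.1% | 4.8% |
| t, Wilcoxon, Friedman | 3.8% | 1.1% | 5.0% |

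The ratios are 2.7/2.1 = 1.3 and, from unrounded rates, 3.83/1.14 = 3.4. The total stays near 5%, so a check of the overall error rate would not reveal the bias.

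*Step 3: lenses coded, smallest p-value still reported.*

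| Tests open | Total |
|---|---|
| t, Wilcoxon | 5.8% |
| t, Wilcoxon, Friedman | 7.8% (3.8% for A, 4.0% for B) |

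Coding restores symmetry. It does not bring the error back to 5%; only naming the test in advance does that.

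**Sensitivity.** With 0 to 100 scores pressed against the upper limit (underlying mean 85), the three-test figures barely move: 3.8% against 1.1% when steered, 7.8% when the smallest p-value is taken. With heavy-tailed differences (t with 3 degrees of freedom) the three-test gap widens to about 4% against just under 1%.

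**Not quantified.** The effect of the end-of-study decision on out-of-window visits depends on how many there are and what they show, which the documents cannot tell.

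**The case against.** - **No promise is broken.** The design is described as masked for the participant, and nothing commits to a masked analyst. A reader might infer that the trial sets up a blind and then abandons it. The documents do not support that. This objection stands.
- **The analyst is not the sponsor.** A university research centre does the analysis. This reduces the concern but does not remove it, since the centre still makes the open choices knowing which lens is whose.
- **Freedom for the primary outcome is uncertain.** The Variable column of Table 6 is blank for both comparison rows in the public text, so the row governing ease of removal cannot be identified. Friedman and Wilcoxon may be an overall test with pairwise follow-up. Repeated-measures ANOVA is visible only in the second row, and the paired t-test is named only for the right-versus-left-eye check. This stands, and it is why the simulated figures are a worst case.
- **Unmasking does not by itself raise the error rate.** It is tempting to cite 5.8% as the cost of an unmasked analysis. That figure comes from taking the smaller p-value and is the same under coded labels. The harm specific to visible identity is the imbalance between directions.
- **Presentation is not inference.** Means or medians and grouped counts are described as ways of presenting data, so the text does not support a claim that they inflate the primary test's error.
- **The remedy is not free.** The same centre generates the schedule, reconciles dispensing logs, enters data and analyses them. Coding needs some separation of roles, and the documents do not show whether that separation already exists.

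**Conclusion.** The point holds as a modest, inexpensive improvement. The plan states that the analysis is unmasked and leaves the tests, further analyses and the handling of out-of-window data open, so knowledge of the sponsor's lens could influence the result. The possible size is an imbalance in false findings of 2.7% against 2.1% with two candidate tests, and up to 3.8% against 1.1% with three. Total error stays at about 5%. These figures assume normal differences, 44 pairs, and listed tests that are genuine alternatives for the primary outcome, which the visible table cannot confirm.

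Two stronger readings should be avoided. The documents do not show that any choice has been or will be steered. Nor would coding alone protect the result: if the test is still picked by its p-value, total error is 5.8% to 7.8%. Coding and a single pre-specified test belong together.

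**What to change.** Replace the unmasked-analysis sentence in Section 12.1 with a short sequence:

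1. Name one test for the primary outcome before any outcome data are seen, with an objective rule if an alternative is to be allowed.
2. The Database Administrator, who generates the schedule, exports the analysis dataset with the lenses coded X and Y. Any other field that would reveal the key is also masked, for example lens brand or base curve (8.7 mm against 8.6 mm in Table 1).
3. Decisions on out-of-window data and other deviations, and any groupings, are made on the coded data.
4. The primary and secondary results are finalised on the coded data, and the key is then released. Later analyses are labelled as done after release.

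The data management plan that Section 12.2 says is still to be developed is a natural place for the export and key-release steps.

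The cost is a recoded export, keeping the key holder separate from the analyst within the centre, and a slightly later release of the key. Sample size, visits and participant burden do not change.
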